6.5 WEEKLY QUESTIONNAIRE

The weekly questionnaire will take approximately 1 minute to complete depending on individual responses to items on sexual behaviour. Weekly questionnaire items include MPX testing, vaccination, diagnosis, and sexual behaviours.^{2,6,34-36}

6.5.1 WEEKLY DIARY INVITATIONS

Participants will be sent an email or text message notification containing an individual, deidentified URL link to their weekly questionnaire every Monday at 5:00 am and are asked to complete their entry within 48 hours. All participants who did not complete their entry within 24 hours will be automatically sent one reminder on the following Tuesday at 5:00 am. Participants who provide their mobile number will receive one final text message reminder on Tuesdays at 11 am.

6.6 BIANNUAL ITEMS

Items relevant to MPX but not needing to be captured as frequently will be asked at baseline, then every six months. These items include questions on STI testing and diagnoses, HIV testing among non-HIV positive GBM, use of antiretrovirals as HIV treatment or prevention, and viral load among HIV positive GBM.

6.7 MPX- DIAGNOSIS

If a participant indicates a new positive MPX diagnosis in a weekly questionnaire, a disease severity and experience module will be enabled. Items included in this module were developed using data from the United States Centre for Disease Control and Prevention and the World Health Organization Global Clinical Data Platform Monkeypox Case Report Form.^{37,38} These items include information on symptoms, severity of infection, and type of vaccination. This will be enabled in the week of diagnosis, and then weekly for 4 more weeks to cover the disease period.

7 RISK TO PARTICIPANTS

It is possible that some participants may experience some anxiety by providing answers about sensitive, personal information, including HIV status and history of other sexually transmitted infections (STI), sexual partners and behaviours, and health-seeking behaviours. Given the association between the current MPX outbreak and GBM, some participants may also be acutely aware of the potential for stigma associated with MPX.

To mitigate against these potential risks, participants will be informed that they have the option of stopping or withdrawing from the study at any point, including partway through completing a survey. In the event that the survey raises any issues for participants, we will provide support contact through the study website and at the end of the survey, including directing participants to lesbian, gay, bisexual, trans, queer and other sexuality, gender, and bodily diverse people (LGBTQ+) specific counselling and support services. Any social harms from participating in this study will be avoided through maintaining confidentiality and distance from both the researchers and our partner organisations.

Based on the research teams extensive experience (sometimes decades) of research in GBMSM+ sexual health, including HIV, we believe participation in this study may also include benefits to participants. Through our longstanding partnerships with LGBTQ+ health organisations, the study team is aware that MPX is a significant health concern among GBMSM+. GBMSM+ in Australia are generally familiar with sexual health research and often willingly volunteer and appreciate contributing to research that might directly benefit their health. Moreover, participants will be able to access information and health resources about MPX provided through our study webpage and at the end of the survey.

8 PRIVACY AND CONFIDENTIALITY

8.1 CONFIDENTIALITY OF PARTICIPANT RECORDS

All information provided by study participants will be maintained in confidence and divulged only as necessary to the ethics committee and institution employees directly involved in the study. Both ethics committee members and employees must also understand the confidentiality requirements for any information divulged to them. The data generated by this study will be considered confidential.

Confidentiality of all data is strictly maintained at all times and in accordance with UNSW Sydney policy. Study data are collected and managed using REDCap, a UNSW Sydney approved data capture platform hosted at the University of New South Wales. At enrolment, participants are required to provide consent to be contacted via an email and optional text message invitation to participate in the online surveys developed using REDCap software. The email address will be entered directly into the e-Consent capture via a secure online enrolment form in REDCap. The secure e-Consent form will store the preferred email address so that the questionnaire system can send participant invitations to complete the questionnaires and send automatic reminders if the participant does not complete a questionnaire within the scheduled timeframe. All identifying information is stored separately from participants' completed questionnaires. Access to any data or identifying information will be protected by secure barriers at each level of access.

Participants are given a unique study identifier which is used to link all data sources. The questionnaires will be electronically coded and stored in a secure REDCap database. Questionnaires will not contain individuals' identifying details. Access to any data or identifying information will be protected by secure barriers at each level of access. The data will only be accessible to the research team directly involved with managing the questionnaires or analysing the data. A password and individualised access name is required to access the database, and an administrator from that site must also have set specific permissions to enable this access. All computers involved with the research are password protected, and access to those computers is restricted to those with a key to locked offices and an electronic security pass that allows access to the building.

Any identifying information that is collected to enable participants to be contacted for follow up is stored on a separate database from the survey, under equally secure conditions (including computer security, password restrictions, physical and site security measures, and access limited only to the research staff). Record matching can only occur through the numerically coded, unique study identifier available only to the investigating researchers. Further steps to safeguard the confidentiality of individual participants are taken at the publication stage by using group data where possible and by changing identifying details where necessary.

8.2 DATA SECURITY

REDCap is a secure, web-based software platform designed to support data capture for research studies, providing:

- 1. An intuitive interface for validated data capture
- 2. Audit trails for tracking data manipulation and export procedures
- 3. Automated export procedures for seamless data downloads to common statistical packages.
- 4. Procedures for data integration and interoperability with external sources.

REDCap has detailed policies on data privacy, backup/redundancy, and disaster recovery. It is compliant and certified under both the EU-U.S. Privacy Shield and Swiss-US Privacy Shield. At regular intervals, these data will be downloaded from REDCap to a secure computer at the Kirby Institute, UNSW Sydney. All electronic databases will be protected by password and UNSW Sydney firewalls. Only designated researchers will have access to databases downloaded from REDCap.

8.3 RECORD RETENTION

The study team will retain all study documents, including essential documents and participant files, for at least 7 years after the completion of the study.

9 ANALYSIS AND STATISTICAL CONSIDERATIONS

9.1 SAMPLE SIZE

9.1.1 VACCINE COVERAGE

Based on a total sample size of unvaccinated men and an expected monthly incidence of vaccination of 5%, following 2000 initially unvaccinated men will give us 80% statistical power to detect a vaccination incidence between 4.1% and 6.0% per month.

Sample size for the estimation of monthly incidence of vaccine coverage, assuming 2,000 or 4,000 initially unvaccinated men are recruited (80% statistical power, 2-sided alpha of 0.05).

Sample size	True monthly incidence of vaccination in the community	Sample size			
Assuming 2,000 initially unvaccinated men recruited					
2,000	1%	0.6 – 1.5			
2,000	5%	4.1 - 6.0			
2,000	10%	8.7 - 11.4			
Assuming 4,000 initially unvaccinated men recruited					
4,000	1%	0.7 – 1.4			
4,000	5%	4.3 – 5.7			
4,000	10%	9.1 - 11.0			

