Recruitment	Community-recruited sample through online platforms, community organisations, and sector partners including Health Departments, including at clinics at which vaccination occurs.
Number of planned participants	 Sample size for the estimation of monthly incidence of vaccine coverage: 2,000. Sample size for the estimation of vaccine efficacy over 12 months of follow-up: 14,949 (3,000 initially unvaccinated and 12,000 initially vaccinated).
Study design	Entirely online, self-directed, self-report prospective observational study.
	Our study is an entirely online self-report observational study of a vaccine uptake and effectiveness. The study team is not involved in the vaccination intervention which is being implemented by state and territory health departments as part of the response to the MPX public health emergency.
Study procedures	This study is an online cohort study and eligibility assessment, consent, and survey completion is entirely self-directed and automated through our data collection system.
	Following consent and enrolment, we will collect data relevant to the research objectives (monkeypox diagnosis and severity, vaccination, risk behaviour) each week for a minimum of 52-weeks and up to 78 weeks depending on date of recruitment. In addition to very brief (< 3 minute) weekly questionnaires, there will be slightly more detailed questionnaires at baseline, 6 and 12 months, and exit survey. Follow-up continues until the last enrolled participant has been followed for 52-weeks.
Study duration	Eighteen months, comprising 6 months of open recruitment and a minimum of 52-weeks of follow-up per participant.

Schedule of assessment

Items	Baseline	Weekly	Six- monthly	Optional one-off modules
Informed consents	Х			
Optional consent	Х			
Demographics	Х			
MPX vaccination	Х	Х	Х	
MPX vaccination tolerability and side effects				Х
MPX testing	Х	Х	Х	
MPX positive diagnosis module				Х
Experience of MPX diagnosis				Х
Sexual behaviours	Х	Х	Х	
COVID-19 infection history	Х			
HIV and STI testing	Х		Х	
ARV use	Х		Х	

Study timeline

		20	22			2023								2024							
	September	October	November	December	January	February	March	April	May	June	ylut	August	September	October	November	December	January	February	March	April	May
Steering committee	٠	•	•	•		•			•			•			٠			•			•
Funding	•	•																			
Ethics approval	•																				
Enrolment	•	•	•	•	•	•	•														
Data collection	•	•	•	•	•	•	•	•	•	•	•	•	•	•	•	•	•	•	•		

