3 STUDY DESIGN

3.1 SUMMARY OF STUDY DESIGN

To address the study objectives, this project will rapidly initiate an entirely online prospective observational study that will systematically survey participants each week for a minimum of 52 and up to 78 weeks to measure the short-term impacts of MPX and to detect trends throughout the MPX epidemic. Enrolment will occur for the first 6 months of the study period. If the epidemic is ongoing after 18 months, further follow-up may be considered. Participants will not be reimbursed for their participation, nor will their participation incur any expenses.

We will systematically follow individual participants each week for up to 18 months (12 months for those participants recruited at the end of month six). The weekly surveys will include questions on MPX testing, vaccination, and diagnosis, while also asking about sexual behaviours, including use of condoms and sexual positioning to determine any associations with the site of MPX infection. Each week, participants who indicate they have had a vaccination or positive diagnosis will answer additional questions, including severity of symptoms and location of infection.

Through the community-recruited sample, we will be able to identify uptake of MPX vaccines by age, sexual risk behaviours, and geographical coordinates (postcode). These data will allow us to identify subpopulations of under-vaccinated communities to inform targeted public health campaigns.

In consenting participants, data linkage will validate self-reported MPX infection and any significant adverse events to MPX infection and vaccination. Consent to data linkage is an optional component to the study.

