9.1.2 VACCINE EFFICACY

Power calculations for vaccine efficacy require an unvaccinated comparison arm. These calculations are made more complex by the fact that most men who are unvaccinated at baseline will become vaccinated as roll-out continues. The pace of this is uncertain, however in the calculations below, we assume that 80% of initially unvaccinated men will become vaccinated over the 12 months.

Sample size calculation for the estimation of vaccine efficacy over 12 months of follow-up. These calculations are for 80% statistical power, 2-sided alpha of 0.05, and assume that 80% of men who are initially unvaccinated become vaccinated by the end of the 12-month follow-up.

Vaccine	MPX	Percentage	Total	Total	Sample size	Sample
efficacy	incidence	initially	number	Sample	initially	size
		unvaccinated		required	unvaccinated	

	in the		of events			initially
	unvaccinated		required			vaccinated
60%	1%	20%	117	25304	5161	20244
		30%	101	20527	6159	14369
		40%	100	19053	7622	11432
	3%	20%	117	8404	1681	6724
		30%	101	6816	2045	4772
		40%	100	6324	2530	3795
70%	1%	20%	56	14949	2990	11960
		30%	51	12459	3738	8722
		40%	53	11838	4736	7103
	3%	20%	56	4965	993	3972
		30%	51	4137	1242	2896
		40%	53	3929	1576	2364
80%	1%	20%	25	8656	1732	6925
		30%	25	7531	2260	5272
		40%	27	7409	2964	4446
	3%	20%	25	2874	575	2300
		30%	25	2500	750	1750
		40%	27	2458	984	1475

Based on the above table, if we assume an MPX incidence in the unvaccinated of 1 per 100 person-years, 20% of participants in the initially unvaccinated arm and 80% of those initially unvaccinated becoming vaccinated by the end of 12-months of follow-up, a total of 14,949 GBM+ followed up for 12- month is required to give us 80% statistical power to detect a vaccine efficacy of 70% in reducing MPX incidence in the vaccinated arm.

As outlined above, this central estimate is that we will require a minimum of about 15,000 participants, about 3000 of whom will be initially unvaccinated and 12000 initially vaccinated.

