10 DISSEMINATION

Similar to the monthly reports provided to NSW Health for the COVID-19 pandemic,^{25,26} we will provide monthly reports summarising key trends in MPX infection and vaccination. This will include MPX vaccination rates stratified by key demographic and behavioural predictors, and MPX incidence rates. Additionally, results will also be disseminated through published reports, journal articles, conference presentations, local workshops, community newspaper/magazine articles, and consultations to professional organisations. The data will also be presented in other media formats if these become available.

Results will be disseminated through published reports, journal articles, conference presentations, local workshops, community newspaper/magazine articles, and consultations to professional organisations. The data will also be presented in other media formats if these become available. In whatever format these data are presented, confidentiality will always be protected as outlined.

Findings will be made available to participants in the same manner as outlined above. Participants are provided this information and how they can access reports of findings on the information sheet. Reports of findings will also be publicised on the Kirby Institute website.

Working in collaboration with national peak body organisations, our results will be disseminated through community public heath campaigns to reach a wider audience. Subject to funding support from government health agencies, this study will produce monthly reports summarising key trends in MPX infection and vaccination. This will include MPX vaccination rates stratified by key demographic and behavioural predictors to inform government health agencies' response to the pandemic.

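### Section 9.1.1's monthly precision holds only for a month with all 2,000 (or 4,000) recruits still unvaccinated and under observation, which six-month accrual and ongoing vaccination do not deliver for most monthly estimates

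*Protocol*

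**What the plan says.** Section 9.1.1 sizes the uptake objective. It states that "following 2000 initially unvaccinated men will give us 80% statistical power to detect a vaccination incidence between 4.1% and 6.0% per month", and its table gives ranges at 1%, 5% and 10% per month, "assuming 2,000 or 4,000 initially unvaccinated men are recruited (80% statistical power, 2-sided alpha of 0.05". Section 3.3 carries the figure of 2,000 forward as the minimum for the coverage objectives.

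Other parts of the protocol determine how many people can contribute to a given month:

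- Section 3.1: "Enrolment will occur for the first 6 months of the study period". The synopsis gives the duration as "Eighteen months, comprising 6 months of open recruitment and a minimum of 52-weeks of follow-up per participant".
- Section 9.1.2, for the efficacy calculation: "we assume that 80% of initially unvaccinated men will become vaccinated over the 12 months". It plans about 3,000 initially unvaccinated participants.
- Section 10: "we will provide monthly reports summarising key trends in MPX infection and vaccination".
- Section 9.2.1 defines the uptake outcome as vaccination incidence per 100 person-years.

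**The concern.** A monthly vaccination incidence has as its denominator the people who are enrolled, under observation and still unvaccinated in that month. The table uses the number ever recruited as unvaccinated. The two differ for two reasons: during the first six months not everyone has joined, and throughout the study each vaccination takes someone out of the risk set. Section 9.1.2 allows for this depletion; section 9.1.1 does not.

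Uptake is a primary objective, the ranges are the stated justification for 2,000 participants, and the monthly reports are meant to inform roll-out. A reader who attaches the printed precision to every monthly report will be overconfident in the early months and again late in follow-up.

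**Working it through.** **Inputs.** N = 2,000, or about 3,000 (sections 9.1.1 and 9.1.2). Monthly rates h of 1%, 5% and 10% (section 9.1.1). Accrual over 6 months and study duration of 18 months (synopsis, section 3.1). 80% vaccinated over 12 months (section 9.1.2). Assumed, because the documents do not say: even accrual of N/6 at the start of each of months 1-6, constant h, no dropout.

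**Step 1: reproduce the table.** Exact (Clopper-Pearson) 95% limits for n × p events among n people:

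| n | 1% | 5% | 10% |
|---|---|---|---|
| 2,000, computed | 0.61-1.54 | 4.09-6.05 | 8.72-11.40 |
| 2,000, printed | 0.6-1.5 | 4.1-6.0 | 8.7-11.4 |
| 4,000, computed | 0.72-1.36 | 4.35-5.72 | 9.09-10.97 |
| 4,000, printed | 0.7-1.4 | 4.3-5.7 | 9.1-11.0 |

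All six agree to within about 0.1 point, so the table takes the full n as the denominator of one month. (These are confidence limits although the text speaks of power. That is a separate matter; the denominator is the issue here.)

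**Step 2: expected number at risk.** R(1) = N/6. R(m) = R(m-1) × (1-h) + N/6 for m = 2 to 6. R(m) = R(m-1) × (1-h) afterwards. For N = 2,000 and h = 5%: R(1) = 333; R(2) = 333.3 × 0.95 + 333.3 = 650; R(3) = 650 × 0.95 + 333.3 = 951; and so on to R(6) = 1,766. Then R(12) = 1,766 × 0.95^6 = 1,298 and R(18) = 1,298 × 0.95^6 = 954.

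**Step 3: same exact limits at those numbers, N = 2,000, h = 5%** (at n = 2,000 the width is 1.96 points).

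| Month | At risk | 95% limits | Width |
|---|---|---|---|
| 1 | 333 | 2.9-7.9 | 5.00 |
| 3 | 951 | 3.7-6.6 | 2.88 |
| 6 (peak) | 1,766 | 4.0-6.1 | 2.09 |
| 12 | 1,298 | 3.9-6.3 | 2.45 |
| 18 | 954 | 3.7-6.6 | 2.87 |

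Month 18 against the stated width: 2.87 / 1.96 = 1.46.

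**Step 4: other rates, each with its own depletion, N = 2,000.**

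- 1% per month: peak 1,951; month 18 has 1,729 (0.6-1.6, against the printed 0.6-1.5). Little is lost once accrual ends.
- 10% per month: month 12 has 830 (8.0-12.2, against 8.7-11.4).
- The constant rate implied by section 9.1.2: h = 1 - 0.20^(1/12) = 12.55% per month, which lies outside the 9.1.1 table. Peak 1,468; month 12 has 657 (10.1-15.3) and month 18 has 294 (9.0-16.9), against 11.1-14.1 at n = 2,000.

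**Step 5: N = 3,000.** At 5%: 500 in month 1, 1,855 in month 4, above 2,000 in months 5-11 (peak 2,649), 1,947 in month 12 (4.1-6.1) and 1,431 in month 18 (3.9-6.3). At 12.55%: above 2,000 in month 6 only (2,202), and 440 in month 18.

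**Step 6: pooled rate.** For N = 2,000 followed for 12 months at 5%, person-months = 2,000 × (1 - 0.95^12) / 0.05 = 18,386, with limits of about 4.7-5.3%.

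**The case against.** The strongest reply has four parts.

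1. **The planned cohort is larger.** A reader might infer that no monthly report will ever have 2,000 at risk. The documents do not support that: section 9.1.2 plans about 3,000 initially unvaccinated, and step 5 shows 2,000 exceeded in months 5-11 at 5% per month. The statement holds only at the 2,000 minimum. The first four months still fall short at 3,000.

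2. **The effect is modest mid-study.** At the peak the limits move by about 0.1 point each, and at month 12 with 5% per month by 0.2-0.3 point. That stands. It is also tempting to put limits for a 5% rate on a risk set depleted at 12.55%, which makes the loss look far worse, but that mixes two rates; step 4 uses one rate per scenario. Section 9.1.2 itself calls the pace of vaccination uncertain.

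3. **Monthly precision may not be the target.** The outcome in section 9.2.1 is a person-year rate, which 2,000 people would estimate more precisely than printed; section 1.2.1 asks for the proportion vaccinated, whose denominator does not deplete; section 10 attaches no precision to the monthly reports. So one cannot infer that 2,000 is too few for the objective. But the table is explicitly about a monthly incidence, so this shows that it does not describe the pooled outcome either.

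4. **This is a planning simplification, not a sum done wrongly.** Agreed: the ranges reproduce. By month since enrolment, all 2,000 are indeed at risk in the first month. What is missing is the condition under which the ranges hold, in a statement that the protocol uses to justify its minimum.

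**Conclusion.** The point holds as a misstatement of precision. The ranges in section 9.1.1 are correct for a single month with the full 2,000 (or 4,000) at risk. At the 2,000 minimum, with even six-month accrual, no calendar month has that many at any of the rates examined. At 5% per month the interval is about two and a half times the stated width in month 1 (5.00 / 1.96), close to it in month 6, and nearly 50% wider in month 18. Faster uptake worsens the late months; at 1% per month little is lost after accrual. With about 3,000 initially unvaccinated the middle months meet or beat the stated precision and the first four do not.

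The month-by-month figures rest on even accrual, constant rates and no dropout; any dropout lowers the numbers further. The study remains feasible and the pooled uptake rate is well estimated, so this is a correction that should be made rather than a threat to the objective.

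**What to change.** In section 9.1.1:

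- State that the printed ranges apply only to a month with 2,000 (or 4,000) people still unvaccinated and under observation.
- Add expected at-risk numbers and 95% limits by calendar month (for example months 1, 3, 6, 12 and 18) for 2,000 and for 3,000 initially unvaccinated. Use one vaccination rate per scenario for both depletion and interval, include the rate implied by section 9.1.2, and state the accrual and dropout assumptions.
- Give the precision of the pooled person-year rate separately, since that is the outcome in section 9.2.1.

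The cost is protocol wording and a recalculated table, with no additional participants or data. The downside is a less favourable stated monthly precision. Pooling sparse early or late months in the reports is an optional reporting choice.

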3.3 NUMBER OF PARTICIPANTS

To address the objectives relating to vaccine coverage, we require a minimum of 2,000 participants. The minimum number of participants needed to address the vaccine efficacy objective is 15,000 (at least 3,000 of whom should initially be unvaccinated). See section 9 for calculations.

The target population for this study is populations considered at high risk of MPX exposure as defined by the World Health Organization's (WHO) interim guidance on vaccines and immunisation for monkeypox.¹⁸ For the purpose of this study, this includes:

- All people (whether cis or trans men, cis or trans women, or non-binary) who
- Report sex with cis and trans gay, bisexual, and other males or non-binary people who have sex with cis or trans men (GBMSM+) in the preceding 12 months.

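### Section 9.1.1 labels 95% confidence limits for monthly vaccine uptake as 80% power; true power at the quoted limits is about one half

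*Protocol*

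**What the plan says.** Section 9.1.1 starts from "an expected monthly incidence of vaccination of 5"% and states that a follow-up of 2,000 men unvaccinated at the start "will give us 80% statistical power to detect a vaccination incidence between 4.1% and 6.0% per month". The table that follows gives ranges for true monthly incidences of 1%, 5% and 10%, with 2,000 or 4,000 initially unvaccinated men. Its caption opens with "Sample size for the estimation of monthly incidence of vaccine coverage" and closes with "80% statistical power, 2-sided alpha of 0.05". No null value or comparator is named apart from the tabulated true incidence.

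Section 3.3 carries the result forward: for the coverage objectives, "we require a minimum of 2,000 participants". The synopsis repeats the figure of 2,000. Vaccine uptake is primary objective 3 (section 2.2).

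**The concern.** A power statement needs a reference rate, an alternative, a sample size, an alpha and a power. A limit derived from 80% power must lie further from the reference rate than the edge of the 95% confidence interval, because it allows for sampling error under the alternative as well. The ranges in section 9.1.1 are too narrow for that. When the true rate sits at the edge of the 95% interval, the estimate falls on either side of the rejection boundary about equally often, so power there is about one half.

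The sample size for a primary objective is therefore justified by an operating characteristic that the design does not have. A reader would take it that a true uptake of 4.1% or 6.0% per month would be told apart from 5% four times in five. The real chance is close to a coin toss.

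**Working it through.** **Inputs, all from section 9.1.1:** n = 2,000 or 4,000 initially unvaccinated; true monthly incidence 1%, 5% or 10%; two-sided alpha 0.05; stated power 80%; stated limits for the main case 4.1% and 6.0%.

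**Step 1: reproduce the printed ranges.** The Clopper-Pearson 95% limits for x events in n are the 2.5% quantile of Beta(x, n−x+1) and the 97.5% quantile of Beta(x+1, n−x). For x = 100 and n = 2,000 they are 4.086% and 6.048%, which round to the printed 4.1 and 6.0. All twelve endpoints are matched this way (table below). For the same case, the 90% interval (4.22% to 5.88%) and the 80% interval (4.38% to 5.68%) do not match. No power value enters the formula, so replacing 80% with any other figure would leave every range unchanged.

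**Step 2: power at the printed limits.** Take the tabulated incidence p0 as the null and the printed limit p1 as the truth. For a one-sample two-sided test:

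power = Φ( [ |p1 − p0| − 1.96·√(p0(1−p0)/n) ] / √(p1(1−p1)/n) )

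With n = 2,000 and p0 = 5%, 1.96·√(0.05 × 0.95/2000) = 0.00955.

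- p1 = 4.1%: (0.00900 − 0.00955)/0.00443 = −0.124, so power is 45.0%.
- p1 = 6.0%: (0.01000 − 0.00955)/0.00531 = 0.084, so power is 53.4%.

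**Step 3: all six rows.** The last column solves the Step 2 formula for 80% power.

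| n | True incidence | Printed range (%) | Exact 95% CI (%) | Power at lower / upper printed limit | Limits with 80% power (%) |
|---|---|---|---|---|---|
| 2,000 | 1% | 0.6–1.5 | 0.61–1.54 | 41.7% / 59.3% | 0.44–1.68 |
| 2,000 | 5% | 4.1–6.0 | 4.09–6.05 | 45.0% / 53.4% | 3.69–6.42 |
| 2,000 | 10% | 8.7–11.4 | 8.72–11.40 | 49.1% / 54.8% | 8.17–11.92 |
| 4,000 | 1% | 0.7–1.4 | 0.72–1.36 | 47.5% / 68.9% | 0.59–1.47 |
| 4,000 | 5% | 4.3–5.7 | 4.345–5.72 | 53.1% / 52.7% | 4.06–5.99 |
| 4,000 | 10% | 9.1–11.0 | 9.09–10.97 | 47.4% / 55.7% | 8.70–11.35 |

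The departures from one half are largest in the 1% rows, where rounding the limits to one decimal matters most. The range printed for 5% with 2,000 men is, to rounding, the 80%-power range for 4,000.

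**Step 4: other readings of the main case (5%, n = 2,000), power at 4.1% / 6.0%.**

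- Exact binomial test, null 5%: 43.9% / 47.6%.
- Null at the limit, truth 5%: 52.5% / 46.7% (exact 47.3% / 48.6%).
- One-sided alpha 0.05: 58.8% / 64.6%.
- Two samples of 2,000 each: 27.6% / 28.3%.

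None comes near 80%.

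**Step 5: sample size for the claim as worded.** n = [ (1.96·√(p0(1−p0)) + 0.842·√(p1(1−p1))) / |p1 − p0| ]², with p0 = 5%:

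- p1 = 4.1%: [(0.4272 + 0.1669)/0.009]² gives 4,357.
- p1 = 6.0%: [(0.4272 + 0.1999)/0.010]² gives 3,932.

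About 4,400 initially unvaccinated men would be needed to cover both sides.

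**The case against.** The strongest defence is that the table is about estimation. Its caption says so, the uptake outcome in section 9.2.1 is an incidence with predictors, and no test against a fixed uptake rate is planned. On that reading the ranges are correct as expected 95% precision, 2,000 is defensible, and only a label is wrong. This stands as far as it goes and points to the simpler remedy. It does not make the 80% power statement true, and that statement is made in both the text and the caption.

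Second, 2,000 is not the binding number. Sections 3.3 and 9.1.2 ask for about 15,000 participants for vaccine efficacy, of whom about 3,000 are initially unvaccinated. That softens the consequence, but the Step 2 formula with n = 3,000 still gives only 63% power at 4.1% and 69% at 6.0%.

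Third, the protocol states no null, so the power figures depend on taking the expected rate as the reference. That is fair, and the exact percentages should be read with it in mind. The match with 95% limits does not depend on that choice, and the alternative readings in Step 4 do not rescue the claim.

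The heading of the table's last column repeats the words used for the first. That may come from text extraction, and nothing here rests on it.

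**Conclusion.** The concern holds. The ranges in section 9.1.1 are 95% confidence limits, and the 80% power attached to them in text and caption is wrong for every row. In the main case (5% per month, 2,000 men) power at the stated limits is 45% and 53% by normal approximation, or 44% and 48% by the exact test; over the six rows the normal-approximation range is 42% to 69%. True 80%-power limits in the main case are about 3.7% and 6.4%, and the limits as stated would need about 4,400 men.

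The power figures assume a one-sample two-sided 5% test against the tabulated rate over a single month, with all n men still unvaccinated and responding. Because the statement is the only numerical support for the sample size of a primary objective, it should be corrected, although the numbers themselves remain usable as precision.

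**What to change.** Choose one of two corrections.

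1. **Precision (simpler, and consistent with the caption's stated purpose).** Say that 2,000 initially unvaccinated participants give an expected 95% confidence interval of 4.1% to 6.0% around an observed 5% per month. Delete the power claim from the sentence and the caption. The ranges and the 2,000 stay.
2. **Power.** Keep 80% power, name the reference rate and the test, and replace the six ranges with those in the last column of the table above. For 5% with 2,000 men the range becomes about 3.7% to 6.4%, a width of 2.7 points against 1.9 now, or about 40% wider.

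Under either option, check that the table's last column is headed as holding incidence ranges.

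Both options change text only and need no extra participants. Extra recruitment would arise only if the sponsor wants 80% power at exactly 4.1% and 6.0%, which takes about 4,400 initially unvaccinated people.
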